4.6 PATIENT WITHDRAWAL AND DISCONTINUATION

Patients have the right to withdraw from the study at any time without needing to give any reason. Should a patient withdraw, all efforts should be made to complete and report observations prior to withdrawal as thoroughly as possible. Patients who choose to discontinue from the study will not be replaced.

The Investigator may withdraw patients in the event of intercurrent illness, AEs, protocol violations, administrative or other reasons. The Investigator is strongly encouraged to contact the Medical Monitor prior to discontinuation of study drug or withdrawal of patient from the study.

Discontinuation of PEX or discontinuation from the study is **mandatory** for:

- Patients whose baseline VO₂MAX is more than ±20% of their screening VO₂MAX, *i.e.*;
(*BASELINE VO₂MAX* – *SCREEN VO₂MAX*)/ *SCREEN VO₂MAX* > ±20%
- Patients who are unable or unwilling to return to the study site to repeat a CPEX test that did not meet the prospectively defined acceptance criteria as determined by the centralized CPEX assessor
- Patients identified as PMs of PEX at the week 1 (day 8) study visit. Despite the screening genotyping, which is 95-97% effective at identifying PMs, there may be a limited number of phenotypic PMs. Phenotypic PM subjects will be identified by determination of the PEX metabolic ratio (MR). This MR is the ratio of CIS to the parent compound, PEX. If the CIS:PEX is <0.4, the patient will be deemed a phenotypic PM regardless of genotype. These patients are at risk for clinically significant elevated plasma PEX levels. Such elevated plasma levels could decrease tolerability or increase the risk of short, self-limited toxicity; if unchecked longer term toxicities could result. Hence, as with the genotypic PMs, these phenotypic PM subjects will be withdrawn from the study. (Patients with a CIS:PEX ratio <0.4 after the week 1 visit will not automatically be withdrawn from the study. These patients should be further evaluated and the patient status will be discussed with the Medical Monitor.)
- Patients with persistent elevations in ALT or AST; see Appendix C for the definition of “persistent”
- Female study participants discovered to be pregnant during the treatment period

Discontinuation of PEX should be considered in the following situations [Phan *et al.*, 2009a] following discussion with the Medical Monitor:

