6.2 SCHEDULE OF ASSESSMENTS

The flowchart of procedures, measurements and other assessments is shown in table 6.2.

Table 6.2 Schedule of Time and Events for Protocol Activities

Complete Schedule of Protocol Activities	Screening [A]	Baseline Week 1 (Day 1) [A]	After Completion of Week 1 (Day 8)	After Completion of Weeks 2, 4, 6, 8, 10, 12 & 14 (Days 15, 29, 43, 57, 71, 85 & 99)	End of Treatment After Completion of Week 16 (Day 113)	Final Visit Week 20 (Day 140)
Time window permitted	-28 days	n.a.	±1 Day	±1 Day for Week 2 ±3 Days for other timepoints	±3 Days	±3 Days
Informed Consent	X					
Inclusion/Exclusion Criteria	X	X [B]				
Demographics, Medical History, Physical Exam	X					
12-lead ECG [C, D]	X	X [E]		X	X	X
CPEX Testing [D, F]	X	X [G]		After End of Week 8	X [H]	
Weight	X	X		After End of Week 8	X	X
Vital Signs [I]	X	X		X	X	X
Laboratory Procedures [J]						
Serum Pregnancy Test [K]	X					X
Urine Pregnancy Test [J, K]		X				
Serum Chemistry [L]	X			After End of Week 8	X	X
Complete Blood Count [M]	X				X	X
Coagulation Tests [N]	X					
CYP2D6 Screening [O]	X					
Plasma PEX, CIS & TRANS [P]			X	X	X	X
Biomarkers (Hemoglobin A1c)	X			After End of Week 8	X	X
Study Dosing & Dose Adjustment as per Guidelines & Algorithm [Q]		Start at 70 mg [R]	X	X		
Review of Dosing Instructions and Adherence to Dosing		X	X	X	X	
Adverse Event Assessment [S]	X	X	X	X	X	X
Adverse Device Effect Assessment [T]			X	X	X	X
Concomitant Medication Review [U]	X	X	X	X	X	X
6 Minute Walk Test (6MWT) [D]		X		After End of Week 8	X	

Footnotes:

- A.** The Screening visit must be performed within 28 days prior to dosing.
- B.** Entry criteria to be evaluated: Baseline CPEX compared to Screening CPEX, and ECG exclusion criteria
- C.** ECGs should be done in triplicate prior to blood draws when possible and obtained after the patient has been resting comfortably in a supine position for approximately 10 minutes.
- D.** ECGs will be done first, the CPEX test will be second, and the 6MWT will be the last procedure completed during any visit by the patient to the study site in order to facilitate the patient's ability to adequately complete a CPEX and a 6MWT in a single day
- E.** The baseline ECG must not meet any of the exclusion criteria detailed in section 4.3.2; this must be confirmed by the central ECG reader before study-drug can be dispensed to the patient
- F.**

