6.7 PERIOD 1; ADDITIONAL PROCEDURES AT COMPLETION OF WEEK 8 (DAY 57) VISIT

In addition to the procedures described above in section 6.6, the following procedures will be completed during the Period 1, Week 8 (Day 57) study visit:

- CPEX testing will be done following completion of the ECG recordings
- Body weight will be measured
- Blood samples will be obtained for routine serum chemistry safety tests and for biomarker levels of hemoglobin A1c
- The 6MWT will be done as the last procedure of the Week 8 visit

6.8 PERIOD 2: END OF TREATMENT AND AFTER COMPLETION OF WEEK 16 (DAY 113 ±3 DAYS)

Dosing should continue through the day prior to this visit. At this visit the following will be completed:

- A 12-lead ECG will be recorded in triplicate; ECGs should be taken prior to CPEX testing or blood draws and obtained after the patient has been resting comfortably in a supine position for approximately 10 minutes
- CPEX testing will be done following completion of the ECG recordings
 - If the centralized CPEX assessor deems the EOT CPEX test to be invalid, the subject may be required to return for a repeat test
- Vital signs and body weight, will be measured; heart rate and blood pressure will be measured in the seated position after 5 minutes of rest
- A blood sample will be obtained for analysis of PEX, CIS and TRANS approximately 12h after dosing on the previous study day
- Blood samples will be obtained for a complete blood cell count, routine serum chemistry safety tests and for biomarker levels of hemoglobin A1c
- Study-drug accountability will be reviewed with the patient. All remaining study-drug will be collected.
- AEs since the patient's previous site visit will be recorded. (As part of the investigation and reporting of all SAEs, every attempt will be made to obtain a blood sample for analysis of PEX, CIS and TRANS as soon as possible after awareness of an SAE.)
- ADEs will be assessed for and recorded
- Concomitant medication used since the patient's previous visit will be recorded
- A 6MWT will be done as the last procedure of the week 16 visit

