6.9 FOLLOW-UP VISIT (FOUR WEEKS FOLLOWING THE CONCLUSION OF DOSING)

At this visit the following will be completed:

- Vital signs and body weight, will be measured; heart rate and blood pressure will be measured in the seated position after 5 minutes of rest
- A 12-lead ECG will be recorded in triplicate; ECGs should be taken prior to blood draws and obtained after the patient has been resting comfortably in a supine position for approximately 10 minutes
- A blood sample will be obtained for analysis of PEX, CIS and TRANS
- Blood samples will be obtained for a complete blood cell count, routine serum chemistry safety tests, a pregnancy test and for biomarker levels of hemoglobin A1c
- AEs since the patient's previous site visit will be recorded. (As part of the investigation and reporting of all SAEs, every attempt will be made to obtain a blood sample for analysis of PEX, CIS and TRANS as soon as possible after awareness of an SAE.)

- ADEs will be assessed for and recorded
- Concomitant medication used since the patient's previous visit will be recorded

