6.11 SUBJECTS WHO WITHDRAW FROM THE STUDY

If a patient chooses to withdraw from the study during the study-drug dosing phase in Period 1 and 2, the study-site will attempt to get the following information before the patient is lost to follow-up:

- Vital signs
- Blood sample for PEX, CIS and TRANS
- Blood sampling for a full blood cell count, routine safety serum chemistry tests, serum pregnancy test and serum levels of hemoglobin A1c
- 12-Lead ECG
- CPEX Testing
- 6MWT
- Treatment Compliance
- Concomitant Medications
- AEs
- Study-drug accountability

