7.7 COLLECTION AND REPORTING OF ADVERSE EVENTS

AEs can be spontaneously reported or elicited during open-ended questioning, examination, or evaluation of a subject. To prevent reporting bias, subjects should not be questioned regarding the specific occurrence of one or more AEs.

If known, the diagnosis of the underlying illness or disorder should be recorded, rather than its individual symptoms. The following information should be captured for all AEs:

- Onset,

- Duration,
- Intensity,
- Seriousness,
- Relationship to investigational product,
- Action taken,
- Treatment, if required.

If treatment for the event was administered, it should be recorded in the medical record. The investigator must supply the Sponsor and the Institutional Review Board/Independent Ethics Committee (IRB/IEC) with any additional information requested, notably for reported deaths of subjects.

Completion of supplemental case report forms (CRFs) may be requested for AEs and/or laboratory abnormalities that are reported/identified during the course of the study.

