7.11.1 Pregnancy Testing

Pregnancy testing will be performed as outlined in Section 6. If the pregnancy of a female study participant is discovered during the treatment period, the study medication should be discontinued.

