3.2.3 Pregnancy Testing

A serum pregnancy test was to be performed at Screening and Week 20, and a urine pregnancy test was to be performed at Baseline (Day 1).

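### No pregnancy test is scheduled during the 112 dosing days, so the mandatory pregnancy stop has no scheduled trigger; a Week 8 urine test would be a cheap safeguard

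*Protocol*

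**What the plan says.** Protocol 4.6 lists the reasons for which stopping drug or leaving the study is mandatory. One is "Female study participants discovered to be pregnant during the treatment period". Section 7.11.1 repeats that drug should be stopped. On timing it adds no test of its own: "Pregnancy testing will be performed as outlined in Section 6".

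Section 6 and the SAP agree on when tests are done. SAP 3.2.3 states: "A serum pregnancy test was to be performed at Screening and Week 20, and a urine pregnancy test was to be performed at Baseline". Protocol Table 6.2 gives the same three occasions, with Week 20 at Day 140. The visit lists in 6.5 to 6.7 contain no pregnancy test. At end of treatment (6.8, Day 113) the blood work is: "Blood samples will be obtained for a complete blood cell count, routine serum chemistry safety tests and for biomarker levels of hemoglobin A1c". The test returns only at follow-up (6.9): "routine serum chemistry safety tests, a pregnancy test and for biomarker levels of hemoglobin A1c". One contingent test exists. When a patient chooses to withdraw during dosing, 6.11 asks the site to attempt "routine safety serum chemistry tests, serum pregnancy test and serum levels of hemoglobin A1c".

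Other safeguards are present. Women not using contraception are excluded (4.3.1 a), and women of child-bearing potential are counselled (7.11). AEs and concomitant medication are reviewed at every visit. AE enquiry works as follows (7.7): "AEs can be spontaneously reported or elicited during open-ended questioning, examination, or evaluation of a subject".

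**The concern.** The other four mandatory stops in 4.6 each rest on a scheduled procedure: CPEX testing for two of them, the Day 8 plasma sample, and serum chemistry at Week 8. Pregnancy can begin at any time during treatment, yet nothing in the schedule looks for it then.

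Contraception and the two tests before dosing make a pregnancy unlikely but do not detect one. The test in 6.11 reaches only patients who are already leaving. A pregnancy that the patient has not recognised could therefore stay exposed until dosing ends and first be tested about four weeks later, when the result can document exposure but no longer limit it. Meanwhile the maximum daily dose rises from 210 mg in Period 1 to 280 mg in Period 2 (Table 4.1). This is a question of participant safety only.

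**Working it through.** **1. Length of the gap.** Dosing is 2 periods × 8 weeks × 7 days = 112 days, which reproduces the plan's figure. From the Day 1 urine test to the Day 140 serum test is 140 − 1 = 139 days, or 136 to 142 with the ±3-day window. Eight visits fall while doses remain (Days 8, 15, 29, 43, 57, 71, 85, 99), and none has a test. The Day 113 visit has none either.

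**2. Doses a positive test could spare.** Visits are in the morning and doses after Day 1 are in the evening, so doses left at Day d = 112 − (d − 1):
- Day 29 (Week 4): 84
- Day 57 (Week 8): 56
- Day 85 (Week 12): 28
- Day 113 (Week 16): 0

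These are ceilings, reached only if the pregnancy is already detectable on that day and not otherwise known.

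**3. Average doses spared per conception.** Assumptions, none from the documents: conception is uniform over the 112 days; a urine test turns positive 14 days later (range 10 to 21); the pregnancy is otherwise unrecognised; drug stops on the day of the positive test. Each test is weighted by the number of conception days it is the first to detect.

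| Lag (days) | Weeks 4, 8 and 12 | Week 8 alone | No gain, three tests | No gain, Week 8 alone |
|---|---|---|---|---|
| 10 | (18×84 + 28×56 + 28×28)/112 = 34.5 | 46×56/112 = 23.0 | last 112 − 74 = 38 days | last 112 − 46 = 66 days |
| 14 | (14×84 + 28×56 + 28×28)/112 = 3528/112 = 31.5 | 42×56/112 = 21.0 | last 112 − 70 = 42 days | last 112 − 42 = 70 days |
| 21 | (7×84 + 28×56 + 28×28)/112 = 26.25 | 35×56/112 = 17.5 | last 112 − 63 = 49 days | last 112 − 35 = 77 days |

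For scale, the mean number of doses taken after conception without any test is 112/2 = 56. At a 14-day lag, 70/112 = 62.5% of conceptions are found with doses left under three tests, and 42/112 = 37.5% under Week 8 alone.

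**4. Expected pregnancies.** The documents do not give the number of women of child-bearing potential. Assume 3 to 10 of the 33 patients, and 1% to 10% per year conceiving despite contraception:
- Low: 3 × 0.01 × 112/365 = 0.0092
- High: 10 × 0.10 × 112/365 = 0.307

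The chance of at least one, 1 − exp(−m), is 0.9% to 26%. The top figure combines both maxima.

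**5. Benefit across the trial.** Multiply expected pregnancies, the share otherwise unrecognised (assumed 25% to 50%) and doses spared per conception at a 14-day lag:
- Three tests: 0.0092 × 0.25 × 31.5 = 0.07, to 0.307 × 0.50 × 31.5 = 4.8 doses
- Week 8 alone: 0.0092 × 0.25 × 21.0 = 0.05, to 0.307 × 0.50 × 21.0 = 3.2 doses

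If every pregnancy went otherwise unrecognised, three tests would spare 0.0092 × 31.5 = 0.3 to 0.307 × 31.5 = 9.7 doses.

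**6. What Week 20 still does.** Day 140 is 139 days after Day 1, so it falls 139 − 112 = 27 days after the end of the dosing interval. Under any lag up to 21 days it can detect a conception at any point during dosing, including those that the added tests miss.

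**The case against.** The strongest case against is that this is a judgement on testing frequency. The stop rule speaks of discovery by whatever route, 7.11.1 defers to Section 6, and the SAP matches. The documents contain no reproductive-toxicity data and no requirement for more frequent testing, so they cannot show that three tests are inadequate. Patients attend nine visits in 16 weeks. Concomitant-medication review could show that hormonal contraception has been stopped. The ban in 7.7 on specific questions concerns AEs, whereas pregnancy has its own surveillance form (7.11.2), so sites may ask about it. The expected benefit is small, and the change needs an amendment.

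Most of this stands. A reader might infer that 4.6 contradicts Section 6, or that the stop rule cannot work. The documents support neither: the rule covers any discovery, and several unscheduled routes can trigger it. A reader might also take 84, 56 or 28 doses as the expected saving. Those are best-case ceilings for a single pregnancy.

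What the objection does not remove is the schedule fact. Every route during treatment depends on the patient recognising the pregnancy or on someone choosing to test. Medication review cannot detect a pregnancy and says little about barrier methods. The visit lists in 6.5 to 6.8 contain no pregnancy question.

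**Conclusion.** The point holds as a low-cost safety improvement to a plan that is internally consistent. It is certain from the documents that no scheduled pregnancy test falls in the 112 dosing days, within a 139-day gap, and that the mandatory stop has no scheduled trigger in that time.

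The benefit is small and rests wholly on assumed inputs: number of women, conception rate, share unrecognised and detection lag. It is about 0.07 to 4.8 doses spared across the trial with tests at Weeks 4, 8 and 12, and 0.05 to 3.2 with Week 8 alone. At a 14-day lag, conceptions in the last 42 days of dosing gain nothing from three tests (38 to 49 days for lags of 10 to 21), and those in the last 70 days gain nothing from Week 8 alone. The case for acting is that an unrecognised exposure, though rare, could be serious, and the check is cheap. No endpoint, power figure or analysis changes.

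**What to change.** For women of child-bearing potential, add the local urine test already used at Baseline to existing visits:
- **Minimum:** Week 8, read before the Period 2 dose adjustment that 4.4.3 places at the end of that visit.
- **Preferred:** Weeks 4, 8 and 12.
- **Keep Week 20**, the only scheduled test that can detect conceptions late in dosing. The reporting window in 7.11.2, counted in half-lives, cannot serve as the reason, because the documents give no half-life.
- A Week 16 test is optional. No doses remain by then, so it would only bring exposure reporting forward by 140 − 113 = 27 days.

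Amend Table 6.2 and its footnote J, protocol 6.6 and 6.7, the SAP schedule table and SAP 3.2.3. The medical team should choose between one and three tests and state how a positive urine result is confirmed.

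Cost: assuming 3 to 10 women, 3 to 10 kits for Week 8 alone or 3 × 3 = 9 to 3 × 10 = 30 for three visits, with no new visit or blood draw. The larger cost is the amendment. It needs IRB/IEC approval before use (10.2) and possibly re-consent at 7 to 10 sites, so it is best bundled with another amendment. Dosing may occasionally be held while a positive result is confirmed. If dosing is already complete, carry the point to the phase III study mentioned in 2.8.

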4.7 CONCOMITANT MEDICATION

Some medications or drug classes are known to have potential for adverse interactions with PEX. They may be used in the protocol, but they should be considered with caution. A list of these agents is included in the Appendix A: Concomitant Medication.

4.8 STUDY MONITORING TEAM

[figure not shown]
A Study Monitoring Team will be established to review and discuss the available study data as patients are enrolled. The team will evaluate all available data listings approximately every two months (until the study is completed) following 25% enrollment in the study. The review will include observed outcomes related to patient safety and tolerance (*i.e.*, AEs, adverse device effects [ADEs], vital signs measurements, ECGs, laboratory assessments, and concomitant medications). These listings will be reviewed by the Study Monitoring Team to determine whether the dosing regimen should be altered during the course of the study or whether any other protocol modifications should be instituted to ensure the safety of the patients. The Study Monitoring Team will include at a minimum an independent cardiologist, the Medical Monitor (CRO), the study biostatistician (CRO), and a Sponsor representative.

5 STUDY DRUG SUPPLIES

5.1 PERHEXILINE

The pharmaceutical formulation contains PEX as its maleate salt (PHM); 2-(2,2-Dicyclohexylethyl) piperidine maleate and its chemical structure is shown in Figure 5.1. The molecular formula of PHM is $C_{19}H_{35}N, C_4H_4O_4$

Figure 5.1 Chemical Structure of PHM (CAS-6724-53-4)

5.2 STUDY DRUG FORMULATION

PEX investigational tablets will be supplied in a dose strength of 35 mg. The study-drug tablets will be packaged and supplied in induction-sealed HDPE bottles with child-resistant closures. The investigational drug products are immediate release tablets containing 35 mg of PEX for every 50 mg of PHM. Excipients include mannitol, microcrystalline cellulose, starch, croscarmellose sodium, talc and magnesium stearate. The tablets are coated with an aqueous, yellow film coat.

5.3 DRUG STORAGE

All study drug required for completion of this study will be provided by the Sponsor or its designee. Upon receipt of clinical trial materials, the study-site recipient will acknowledge receipt of the drug indicating shipment content and condition. Damaged supplies will be replaced. The Investigator or designee will inventory supplies and return appropriate copies of the shipment receipt form to the Sponsor and/or the drug supply vendor. The Investigator will maintain study drug in a pharmacy or locked and secure storage facility with a temperature control monitoring system, accessible only to those individuals authorized by the Investigator to dispense the study drug. The study drug should be stored at controlled room temperature from 15°C to 25°C with an allowed range up to 30°C for short time periods.

5.4 STUDY-DRUG DISPENSING AND DOSING INSTRUCTIONS

It is the responsibility of the Investigator to ensure that investigational product is only dispensed to study patients. The investigational product must be dispensed only from official study sites by authorized personnel according to local regulations. All material not dispensed to patients must be accounted for and retained at the study site until the conclusion of the trial when the sponsor authorizes the destruction or return of material. The names and signatures of site personnel authorized by the Investigator to dispense study drug must be documented on the site personnel log, or other appropriate form.

Patients will be given instructions on the number of tablets to take in each dose and on the timing of dosing. All study-drug dosing must be completed in the evening (preferably 8-11p.m.) on every day of dosing (with the exception of the first dose of study drug, which will

be administered under the supervision of the study-site staff). Patients will record daily dosing (number of tablets taken) on each day in a patient diary designed for that purpose. In addition, the patients will record the time of dosing on the day prior to study-site visits to facilitate the calculation of the time of blood sampling (approximately 12h after dosing) for the determination of systemic study-drug levels. It is the Investigator's responsibility to ensure, at each study visit, that patients understand these dosing requirements.

Patients will be instructed to store their dispensed study-drug supplies at ambient room temperature and to take precautions to ensure that those supplies do not experience extremes of temperature (e.g., not to store in a refrigerator, not to leave the study drug in their car or near a window where it may be exposed to direct sunlight and or heat for a prolonged period of time).

5.5 WITHDRAWAL OF PERHEXILINE AT STUDY TERMINATION

At completion of study-drug dosing or premature withdrawal, diabetic subjects who require hypoglycemic agents should be cautioned that the need for an increase in dosage of the hypoglycemic medications may be required when PEX is discontinued.

